Step 2. We surveyed the country with guidance from Ministry of Health publications and consultations, and excluded districts that have or recently had an active maternal health or newborn health intervention, as this would dilute the effect of our intervention or result in high levels of quality of birth care at baseline, with little room for improvement.

Step 3 We combined Western and Southwest Regions into one group and Eastern and East Central Region into a second group in order to consolidate as Western had only 4 possible districts and East Central had only 3.

Step 4. We examined the a) number of facilities by type in each district and b) caseload of births in one year (July 2012- June 2013) in each district, and calculated the average number of births per facility per day. We then selected all districts within the two groups that had an average of > or = to one birth per facility per day. This resulted in 6 districts in the Eastern group and 6 in the Western group.

All public Level II, III, and IV facilities offering birthing services within a district will be included (range of 7-17 per district for a total of 133 facilities). In districts where there is no public hospital, we will include any Private Not for Profit hospital providing birthing services in that district where they exist. In all of these facilities, as mentioned in Section 3c, an estimated 1,300 providers will be included in the study.

District assignment to intervention arm:

In each region we will divide the six districts into two groups of three. Within the groups of three we will randomly choose a district name from a hat. For the district pulled we will draw a number card with a “1”, “2”, or “3” from a hat. Those numbers will correspond with the study arms outlined in Table 1 (page 2).

- Describe the study participants and the population from which they will be/were drawn. If you plan to include children, specify their ages and gender.

Study participants include any providers at selected facilities who provide birthing services to women and all women admitted to the labor ward for labor. (Table 2 presents the maximum number of study contacts per participant.

Table 2. By research objective, Participants (Sample and Population), Data Source, and Number of Contacts

Obj.	Study Participants (Sample & Population)	Data Source	Number of Study Contacts

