2	Facility in-charge or designated provider/pharmacist	Health facility assessment checklist;	Total: 3 (Baseline, Midline, Endline)
2 and 3	Providers in health facilities who attend births on days and are present on days of training and/or assessment/observation [Population: providers who attend births]	Written knowledge tests and OSCE competency tests for BAB and HBB using simulators	Before and after BAB training Before and after HBB training day Midline assessment Endline assessment Total: 4
		Direct Clinical Observation (DCO) of births at facility	Total: 3 (Baseline, Midline, Endline); providers may be observed several times over the course of the 2 or 3 day assessments
3, 4	Women giving birth in health facilities on days of observation, and newborns [Population: women giving birth and their newborns]	Direct Clinical Observation (DCO) of births at facility	1 (women will likely be observed only with one birth over the period of the study)
4,5	All women who give birth in study facilities (and newborns) will have their service delivery statistics recorded (without identifiers) and aggregated	Abstraction from Facility registers (existing registers and supplemental information for the HMS:BAB and HBB project)	None
1, 2	Providers described above who are selected to be Peer Practice Coordinators (PPC) who attend births and are selected to be PPCs due to leadership skills [Population: see	PPC practice logs	Weekly, the PPC will record data in the practice log.

Obj.	Study Participants (Sample & Population)	Data Source	Number of Study Contacts
	above]		
1	Providers, Facility In-charges, and stakeholders such as Ministry of Health in-charges	Semi-structures interviews	1
1	Providers	Focus group discussions	1

b. Describe any screening procedures and any **inclusion or exclusion criteria**.

For Providers:

- **Inclusion Criteria:** Health providers who attend births in participating health facility and consent to be assessed at the time of enrollment and at several points in time over two years.
- **Exclusion Criteria:** none

For Peer Practice Coordinators:

- **Inclusion criteria:** criteria for being a PPC include: being an experienced skilled birth attendant and likely to remain at the facility during the study period
- **Exclusion Criteria:** Provider has <1 year of experience, and has plans to be transferred to another facility or leave the facility soon.

For Women in Labor and Delivery and Newborns - Observations of Births

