- **Inclusion Criteria:** Women in any stage of labor in participating facility who consent to observation of their delivery and care of their newborn (or consent from the next of kin if the woman is incapacitated and not able to provide consent)
- **Exclusion Criteria:** none

Facility In-charges and Stakeholders

- **Inclusion Criteria:** Facility in-charges at sampled health facilities; stakeholders identified by Jhpiego senior managers as being influential in maternal and newborn health policy decisions in Uganda.
- **Exclusion Criteria:** none

c. Provide **sample size** and a **justification** as to how you arrived at your projected sample size.

The total sample size for this study is 4683 - 2604 health care providers plus 2079 laboring women.

Knowledge and Competency Assessments

For the knowledge and clinical practice assessment, we propose conducting a census of birth attendants working at each facility on the days of training and midline and endline facility data collection. In training interventions, it is routine to test participants before and after the intervention in order to give them feedback to clarify any misunderstandings and improve their performance. We will also do these assessments at baseline and midline facility data collection because we are also interested in collecting data from all providers so that we can do a secondary analysis that will test for a correlation between providers' performance on knowledge assessments and simulator-based performance tests, participation in practice sessions, and directly observed clinical performance. Table 3 presents the maximum number of providers in

the sample facilities, based on data provided by the Ministry of Health; actual enrolled numbers will be lower because not all health care providers on staff will present on the day of data collection. **In addition, we recognize there will be overlap between providers at each time point.** The outcome measure will be a continuous variable measuring ‘correct’ knowledge and competencies across three OSCE exams of BAB or HBB.

Table 3. Number of Providers to be Assessed (c)

Region	Pre and post BAB training (a)	Pre and post HBB Training (a)	Midline Assessment (b) (d)	Endline Assessment (b) (d)	Total Providers in each study group (e)
Districts in Eastern	253	253	253	253	1012
Districts in Western	398	398	398	398	1592
Grand Total	651	651	651	651	2604

Notes

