Service statistics for deliveries and newborn care will be collected from the monthly aggregate reports that do not have the client names (no identifiers).

Providers:

Identifiers will be collected from health providers observed in clinics and/or trained. Provider identifiers will be stored in a database that will be separate from the database storing information about provider knowledge and performance. Rationale: We will follow individual providers over time to track increase in performance or competencies. We need to be able to identify unique providers, such as by collecting name, date of birth, cadre, and health facility, in order to link the data collected on the same provider at various time points (longitudinal analysis). In one study arm providers will be invited to share their mobile telephone number in order to receive content and practice reminders. We will collect no identifiers from providers that participate in focus group discussions.

Facility in-charges and stakeholders:

We will collect no identifiers from those asked to participate in the semi-structured interviews.

Does your study fall within HIPAA requirements because of either of the following:

- 1) The study team will access, collect, and/or use for research purposes protected health information disclosed by a U.S. health care provider (covered entity), or
- 2) Identifiable private health information collected elsewhere (including from a foreign country) will be brought to a covered entity here in the U.S. (for example, a JHU SOM laboratory) for analysis?

No. Jhpiego is not a covered entity because it does not provide health care, health insurance or services related to health care billing.

4. Study procedures:

- b.** If your study involves contact, direct or indirect, with subjects, provide the following:
 - 1) General **study design and methods.**

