After a 2-month period of LDHF practice and consolidation of learning, the second one-day training intervention for newborn asphyxia will take place in the facility.

Intervention: Helping Babies Breathe

The second module, “Helping Babies Breathe” (HBB), is designed to increase newborn survival by improving recognition and basic interventions for babies who do not breathe at birth. HBB focuses on routine care after healthy birth, initial steps of help to breathe at birth, ventilation with bag and mask, and ongoing care after resuscitation. Again, to ensure retention and improved performance, for two of the study arms (the same two as above) training will be followed by ongoing LDHF simulation practice conducted by the same PPCs at the facility who were trained to provide LDHF practice support after the PPH intervention (the 3rd study arm will have the newborn simulator left at the facility with a recommended schedule for practice.) As above, the intervention arm receiving the mobile phone support for PPH will receive mobile phone support for newborn resuscitation.

During the intervention period, the investigators will work with ministry of health officials to ensure adequate supply of oxytocin, and supplies related to neonatal resuscitation.

Evaluation Activities:

Data collected at baseline, midline and endline include: facility assessment, provider knowledge and skills assessment (using a simulator), and direct clinical observation. Baseline data will be collected before the one-day training in BAB. Midline data will be collected after the training and 8-weeks of practice for BAB and HBB, plus the 4 weeks of combined practice. Endline data will be collected six months after the end of the combined practice sessions.

Times of Data Collection

- Data will be collected at the facilities (facility readiness assessments and observation of provider performance) at baseline prior to any intervention that involves providers or

training. Each visit will take place over 2 or 3 days to a health facility. During this baseline visit time the provider knowledge tests and skills stations (OSCEs) for HMS:BAB and HBB will also be administered.

- On the day of training, data will be collected pre and post-training from training participants. This includes knowledge and OSCEs. BAB and HBB trainings will occur separately at different times.
- Following training and during approximately five months of the active intervention phase:

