The primary independent variable will be the study group represented as 2 indicator variables for full and partial training package with training-only as the reference group. For these hypotheses, we will only use endline data. Additional variables, related to provider- and facility characteristics predictive of these outcomes, such as cadre, number of years of provider's experience, and number of prior births attended in last 90 days, will be also included in the model. Analysis of residuals will inform whether the assumptions of the generalized linear model, such as normality and homoscedasticity of residuals as well as linear fit, are satisfied.

Additional analyses will include:

1. At baseline, midline and endline we will collect data from **all study facilities** consisting of service delivery statistics, and facility inventory. These data will be analyzed using population-average marginal generalized linear models estimated using generalized estimating equations (GEE) with exchangeable working correlation structure to account for repeated observations within facilities. The dependent variable will be service delivery statistics. The independent variables will include time (represented as 2 indicator variables for midline and endline with baseline as the reference group), study group (represented as 2 indicator variables for full and partial training groups with training-only as the reference group), and interaction terms (study group by time). The interaction terms will be examined to assess whether there are differences between study groups that change significantly over time.
2. Providers who are trained will keep **logs of their practice sessions**. This is process evaluation data. These data (for example on number of times a scenario is practiced) will be compared across the three study groups using generalized linear models with Poisson or Negative Binomial distribution for the outcome.
3. **Routinely collected data from health facility registers** (recorded daily but aggregated monthly) on services provided to clients and health outcomes (discharge, or deaths and stillbirths) will be analyzed using longitudinal data analysis to account for repeated observations at each facility. This will be for population-averaged marginal generalized linear models using generalized estimating equations (GEE) and exchangeable working correlation structure.

Qualitative Analysis

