Data Source	Research Burden
Health facility assessments	
Direct clinical observation (DCO)	Observations of care during labor and delivery and the immediate newborn period will not entail a research burden. No additional time of the providers or women is involved, except for the time needed to explain the study and obtain informed consent.
Knowledge and competency assessment (OSCE) of providers	This will take 60 minutes. Pre- and post-training assessments are standard procedure during training workshops, and are expected by providers who participate in training. They will also be collected at midline and endline.
Peer practice coordinator (PPC) weekly logs	This may involve a 30 minute burden per week.
Abstraction from Facility registers (existing registers and supplemental information for the HMS:BAB and HBB project)	Health facility registers will be modified to collect data related to post-partum hemorrhage and newborn care. The registers will record data on routine services that are to be provided to all mothers and newborns. Registers may also collect data on the care provided to cases, to clients with PPH and newborn asphyxia. There may be separate registers for deaths. Any modifications to standard registers or supplemental registers will be approved by MOH and district authorities. Participating providers may spend an extra 30 minutes per week documenting services provided and outcomes of the patients.
Focus group discussions	Up to 1 hour
Semi-structured interviews	Up to 30 minutes

e. Describe how participant **privacy will be protected** during data collection if sensitive questions are included in interviews.

This study does not collect sensitive information. Observations will occur where services are normally offered to women in labor and delivery wards. Observers will be as unobtrusive as possible.

During pre and post-training assessments, providers will be assessed in private, in a way that other providers cannot see or hear the simulations, and data when assessments are taken will be kept confidential.

Registers on services provided to patients will be kept as they normally are in the facilities.

9. Benefits:

a. Describe any **potential direct benefits to participants** from participating in the research (not including payment for participation)

Benefits to Providers

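### The Hypothesis 3 and 4 models for knowledge and OSCE scores name no pre-intervention score, and the protocol disagrees with itself on whether a baseline-visit score will exist

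*Combined protocol and SAP*

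**What the plan says.** Section 4b5 (Hypotheses 3 and 4) fits generalized linear models to four endline outcomes. The first is the knowledge and competency score. Arm enters as two indicators with training-only as reference, and the text adds: "For these hypotheses, we will only use endline data". Provider and facility characteristics that predict the outcome are also to be included, with cadre, years of experience and births attended in the last 90 days given as examples. No earlier test score is mentioned.

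On whether such a score exists, the protocol gives two accounts.

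- **Tested at the baseline visit.** Section 4b2 (Times of Data Collection): "During this baseline visit time the provider knowledge tests and skills stations (OSCEs) for HMS:BAB and HBB will also be administered". Section 3c (Knowledge and Competency Assessments): "We will also do these assessments at baseline and midline facility data collection".
- **Not listed at the baseline visit.** Table 2 gives the test contacts as "Before and after BAB training Before and after HBB training day Midline assessment Endline assessment", four in total. The columns of Table 3 follow the same four occasions. Section 8d describes pre- and post-training testing and adds "They will also be collected at midline and endline".

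Linkage is foreseen. Section 3d collects provider identifiers "in order to link the data collected on the same provider at various time points (longitudinal analysis"). Section 3c expects staff to be only partly the same over time: "we recognize there will be overlap between providers at each time point". Section 4b5 classes knowledge and competence as secondary outcomes, but Hypotheses 3 and 4 name the competency level explicitly.

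**The concern.** A provider's own earlier score on the same test is usually one of the better predictors of the later score. If the baseline-visit tests are given, the plan collects that predictor, can link it, and then does not name it in the arm comparison.

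Two things are at stake. One is precision for a comparison that has no stated power: Section 3c gives no SD, target difference, ICC or power for the scores. The other is protection against chance differences at the start. Section 3 draws districts to arms within four groups of three, which leaves four districts per arm, and an endline-only model makes no correction for an unlucky draw in prior skill.

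The point is confined to the score models. The birth outcomes come from different women at each time point, so they have no individual baseline value to adjust for.

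**Working it through.** **No plan figure to reproduce.** The provider sample is a census. The ICCs of 0.005 and 0.01 in the notes to Table 5 belong to the oxytocin outcome. Every correlation and ICC below is therefore an assumption.

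**1. Chance imbalance.** With four districts per arm and district ICC d, the SD of the chance district-level difference between two arms, in score SDs, is √(2d/4).

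| d (assumed) | SD of difference |
|---|---|
| 0.01 | 0.07 |
| 0.05 | 0.16 |
| 0.10 | 0.22 |

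**2. Gain at provider level, full linkage.** Against a model with no covariates, the variance falls by r², where r is the baseline-endline correlation. That is the wrong comparator, because the plan already includes covariates. Suppose these together correlate c = 0.4 with each score. The correlation left for the baseline score to use is (r − c²)/(1 − c²), and its square is the further fall in variance.

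| r | Against no covariates, r² | Partial correlation | Further fall |
|---|---|---|---|
| 0.3 | 9% | (0.30 − 0.16)/0.84 = 0.167 | 2.8% |
| 0.5 | 25% | (0.50 − 0.16)/0.84 = 0.405 | 16.4% |
| 0.7 | 49% | (0.70 − 0.16)/0.84 = 0.643 | 41.3% |

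**3. District component.** Let R be the district-level correlation between baseline and endline, r the within-district slope, and m the providers per district. With total score variance 1:

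- without the score: V0 = (2/4)[d + (1 − d)/m]
- with the score: V1 = (2/4)[d(1 − 2rR + r²) + (1 − d)(1 − r²)/m]

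The district term shrinks only if R exceeds r/2. The unfavourable corner of the assumed range is r = 0.7, R = 0.3, d = 0.10, where 1 − 2rR + r² = 1.07.

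- m = 651/12 = 54.25 (Table 3): the brackets are 0.1166 and 0.1155, a fall of 1.0%.
- m = 1,300/12 = 108.33 (Section 3, "an estimated 1,300 providers will be included in the study"): the brackets are 0.1083 and 0.1112, a rise of 2.7%.

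Less extreme pairs (r = 0.6 with R = 0.4; r = 0.4 with R = 0.6) give falls of 13.8% to 30.8% over d = 0.01 to 0.10 and both values of m. V0 has no covariates, so all these figures show direction and overstate the gain over the actual plan.

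**4. Partial linkage.** A simulation with 60% of providers linked at random, 55 per district, d = 0.01 and r = R = 0.5 gave a fall of 14.8%, against 25% from the formula with full linkage. It filled missing scores with the facility mean, carried a missing-data indicator, and compared with an unadjusted contrast, so it too shows direction only.

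**5. Why no missing-data indicator.** Staff who arrive after allocation have no baseline score, and turnover may differ by arm. Suppose 40% of endline providers are newcomers in training-only and 30% in the full package, newcomers score 0.5 SD lower, and the arm difference among both newcomers and established staff is 0.30 SD. The difference over all endline providers is 0.30 + 0.5 × (0.40 − 0.30) = 0.35 SD. A model with the indicator returns 0.30 SD, which is a different quantity. Restricting the analysis to linked providers conditions on the same feature.

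**The case against.** The best defence is that the plan does not rule the score out. Section 4b5 is headed as a brief plan, its covariates are given as examples of predictive characteristics, and the endline sentence may limit only which outcome records are analysed. The scores are secondary, and the benefit rests on correlations that the protocol does not give. This largely stands, and it is why the point is an improvement and not a fault in validity. What remains is that a strong candidate covariate should be named in advance, and the endline sentence points away from it.

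It is also fair that the gain is easily overstated, since cadre, experience and recent births already carry part of the same information. Step 2 allows for this. The one case in which precision worsens needs 108 providers per district, while Section 3c describes the 651 of Table 3 as a maximum.

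A reader might infer more than this. One inference is that endline-only analysis biases the comparison. The documents do not support it: districts are drawn at random to arms, so the endline contrast is unbiased on average. Another is that the plan discards around half the available precision. That takes the top of an assumed range, full linkage, and a comparator without the planned covariates. A third is that an endline model cannot address an outcome described as change. With randomly drawn districts, the arm difference at endline and the arm difference in change have the same expectation.

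**Conclusion.** The point holds as a cheap improvement to the score models. The planned Hypothesis 3 and 4 contrast is valid without the baseline score; what is lost is some precision and some insurance against an unlucky draw of four districts per arm.

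The size cannot be settled from the documents. At provider level, with full linkage and planned covariates assumed to correlate 0.4 with each score, the variance falls by about 3%, 16% or 41% at r of 0.3, 0.5 or 0.7. Partial linkage makes the gain smaller. If the district-level correlation is well below the provider-level one, the gain could be close to nil or slightly negative.

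The firmest part is documentary. Sections 3c and 4b2 schedule a baseline-visit test that Table 2, Table 3 and Section 8d do not show. Until that is settled, nobody can say whether a pre-intervention HBB score will exist.

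**What to change.** 1. Reconcile Sections 3c and 4b2 with Table 2, Table 3 and Section 8d on whether knowledge tests and OSCEs are given at the baseline visit.
2. If they are, keep the endline score as the outcome and keep every endline provider in the model. Add the provider's own baseline-visit score on the same test as a covariate, and reword the endline sentence so that it limits outcome records only.
3. Fill a missing baseline score with the facility's baseline mean, without a missing-data indicator.
4. Report the model without the score alongside, as the sensitivity analysis. An analysis of linked providers only is at most descriptive.
5. If no baseline-visit test is done, use the BAB training-day pre-test for BAB scores only. Do not use the HBB training-day pre-test: under Section 4b1 it follows eight weeks of BAB practice that differs by arm.

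The cost is one provider-level covariate, a filling rule and one extra model. No new data are needed if Section 4b2 is followed, and no district-level degree of freedom is spent. There may be a small loss of precision in unfavourable cases. The birth-outcome models stay as planned. The adjustment does not replace accounting for clustering by district.
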